^c Face images taken at 09:00, 14:00 and 19:00 each day.

^d The 2-day window pertains to all Visit 3 tasks except the NRS symptom scores, face images, QoL-OHIP and Global assessment which should be collected at their respective nominal times (±60 minutes) on Day 14.

^e Face image(s) and NRS symptom score(s) required if a new outbreak of herpes labialis is suspected by the investigator.

^f After successful completion of all screening procedures.

^g Follow up dates established using the Day 1 dosing date.

Version 5.0 Page: 20 of 68

2. Introduction

Herpes labialis (HL), also called cold sores of the lip, is an infection primarily caused by herpes simplex virus type 1 (HSV-1) and occasionally herpes simplex virus type 2 (HSV-2). The infection is typically spread between people by direct contact. HL is a rash of the skin and mucous membranes (in particular, the lips) and is characterized by erythema and blisters that are preceded and accompanied by tingling, itching or burning pain [1].

For an infection to manifest, the virus must come in contact with mucosal surfaces or abraded skin. The viral replication takes place at the site of primary infection (epithelial cells), either as an intact virion or the capsid is transported in a retrograde fashion by neurons to the dorsal root ganglia, where, after another round of viral replication, latency is established. After primary infection, the virus recedes via the sensory nerve into the respective ganglion (usually the trigeminal ganglion), where it lies latent throughout the individual's lifetime. Stimuli such as fever, menstruation, sunlight, and upper respiratory infections can reactivate the virus, after which it returns to the epithelial cells via the sensory nerve [2].

HSV1 and HSV2 infections rest in a dormant (inactive) state until the virus is activated. During an active phase of infection, a visible outbreak of sores may be observed. Infrequently, life-threatening infection (e.g., encephalitis) may occur. The more severe the primary infection (as reflected by the size, number, and extent of lesions) the more likely it may be that recurrences may develop when triggered [3,4].

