8.1.4 Treatment/Evaluation Phase (Day 1)

Participants who start to experience prodromal symptoms before the visible appearance of any signs of HL must document the start time of symptoms in Science 37 Platform, complete a pre-dose (immediately before dosing) 0-10 NRS cold sore symptom evaluation (pain, burning sensation, itching and swelling) and a face image. Prior to the start of study intervention, all WOCBP participants MUST perform a urine pregnancy test, and verify that the results are negative (not pregnant), and record in the Science 37 Platform. After verification of a negative pregnancy test result, the participant may self-initiate study intervention.

Any participant who has a positive pregnancy test or is not sure of the results must contact the Science 37 study team immediately. Participants with a verified positive pregnancy test must not self-administer study intervention and will be withdrawn from the study.

Participants must always record pre-dose NRS and a face image irrespective of the start time of prodromal symptoms in the Science 37 Platform. After the completion of all pre-dose procedures, participants will be instructed to self-administer one (1) tablet. Should the buccal tablet adhere to the upper gum correctly, a second dose/tablet is NOT applied. A second tablet in the treatment kit is provided and labeled "BACKUP". The backup tablet should only be used if an issue occurs applying the first tablet (see Section 6.5).

After dosing, participants will complete the 0-10 NRS cold sore symptom evaluation, and face images at 09:00, 14:00 and 19:00 that day within Science 37 Platform. Depending on time of day study intervention is started, some Day 1 assessments and face images may not be collected if the time (minus the 60 minute window) occurs before the time of dosing. If dosing is started after 19:00, then post-dose NRS and face images will be collected starting the next day at 09:00. All post-dose time point assessments (NRS and face images) have an allowable window of ± 60 minutes.

Version 5.0

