2.2 Study Design

This is a randomized, multi-center, subject-initiated, double-blinded, single treatment study comparing acyclovir 50 mg muco-adhesive buccal tablet (Sitavig) to matching placebo in the treatment of HL in immunocompetent adults.

The study consists of a Screening and Randomization Phase, Run-in Phase, Treatment Phase/ Evaluation Phase, and a Follow-Up Phase.

Screening/Randomization Phase:

Subjects will be screened for eligibility up to 35 days prior to study according to the inclusion/exclusion criteria. Eligible subjects will be randomized into one of two study interventions. Subjects will then enter into Run-in Phase, which starts a six-month treatment eligibility window.

Run-in Phase:

The Run-in Phase is a six-month treatment eligibility window that provides the opportunity for subjects to spontaneously start an HL outbreak that would require treatment. Subjects will be in contact with Science 37 using weekly virtual check-ins within the Science 37 Platform. Adverse events and concomitant medications could be recorded. Subjects who do not develop an HL episode within six months will be withdrawn from the study.

Treatment Phase/Evaluation Phase:

Once subjects experience prodromal symptoms, they will take face images and self-initiate treatment (study intervention) preferably within one hour and before the visible appearance of any signs of HL lesions according to the product instructions. Subjects will also be completing HL symptom scores (pain, tenderness, itching, tingling and discomfort) as well as QoL scoring using the Oral Health Impact Profile (OHIP) and during the next 10 days within the Science 37 Platform. Subjects will then be under evaluation for healing of the primary lesion(s) up to 14 days.

CONFIDENTIAL Page 9 of 31

Private and Confidential Study No 21755 Date: DEC 18, 2023

Subjects will be asked to meet with the clinic via the Science 37 Platform within 36 hours of the start of study intervention (Day 1) and complete face images, symptom and QoL scores using the Science 37 Platform. Additionally, subjects will complete face images, symptom and QoL scores on Days 2 through 13 with a virtual visit on Day 14 (+2 days), Visit 3 using the Science 37 Platform.

Follow-up Phase:

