3.3 Handling of Missing Data

For subjects whose HL lesions are healed, however, healing ending date and time are missing, DOE and time to cessation of symptoms will be imputed as 14*24 hours since the observation period to determine healing can last up to 14 days.

To handle missing or partial dates, the following rules will be applied.

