4 DEFINITIONS AND DERIVATIONS

Run-in Failures: Run-in failures are participants who successfully completed screening and randomized to a blinded study intervention (treatment). Participants start a 6-month eligibility window during the Run-in Phase where they could potentially self-initiate treatment. Participants who are considered a Run-in failure occur because of the following:

- Randomized participants with no prodromal symptoms after 6 months
- Met an exclusion criterion (e.g., medication, pregnancy)
- Adverse event or change in medical history that requires study withdrawal
- Withdraw of informed consent by the participant
- Study intervention kit not available
- Lack of compliance as determined by the Investigator/designee

Baseline: Baseline value is defined as the last non missing assessment prior to first administration of the study drug. If the assessment occurs on the same day as the first study drug administration, then the time of assessment should be compared to the time of first dose administration to derive the baseline value.

Post-baseline: The Post-baseline values are defined as assessments taken after the first administration of study drug/treatment.

Change from Baseline = $(post\ baseline\ value - baseline\ value)$.

Duration of Episode (DOE): DOE is defined as the time from the initiation of treatment to the healing of primary lesions (loss of crust) for subjects who experience a vesicular lesion. For subjects whose primary lesions are not vesicular in nature, DOE is the time from study intervention initiation to the return to normal skin as determined by the independent blinded reader of the subject's face images using a 6-point Likert scale or the cessation of symptoms, whichever comes last. For the subjects who do not demonstrate the healing of primary lesions or cessation of symptoms, the data will be censored at 14 days (14*24 hours) regardless of any circumstances. If time (hour) is missing for either treatment initiation or the healing of primary lesion or both, however, both dates are recorded, then DOE is number of days (end date – start date) *24. If only healing ending date and/or time are missing, DOE will be imputed as 14*24 hours. If date of treatment initiation is missing, then DOE will be missing.

CONFIDENTIAL Page 17 of 31

Private and Confidential Study No 21755 Date: DEC 18, 2023

DOE (hours) = (Date and time of healing of primary lesions – Date and time of first treatment administered)

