Vesicular lesion: A lesion will be categorised as vesicular if a subject has face image interpretation Likert scale score of 3 or above.

Healing of primary lesions: A vesicular lesion will be considered as healed if the face image interpretation Likert score drops to either 0 or 1 after progressing to 3 and beyond. For those without a vesicular lesion, healing is defined as a face image interpretation Likert score of 0 or cessation of symptoms i.e., all NRS symptom scores as 0, whichever comes last.

Cessation of symptoms: Cessation of symptoms is defined as the absence of sensations of pain, tenderness tingling, itching or discomfort at the site of the cold sore as measured by NRS. In other words, having the NRS score of 0 for all symptoms such as pain, tingling, tenderness, itching and discomfort is cessation of symptoms.

Time to cessation of symptoms: It is the time (in hours) from the initiation of treatment dose of assigned study intervention to cessation of symptoms. For the subjects who do not demonstrate the cessation of symptoms, the data will be censored at 14 days (14*24 hours) regardless of any circumstances. If hour is missing for either treatment initiation or the endpoint but both dates are recorded, then Time to cessation of symptoms is number of days (end date – start date) multiplied by 24. If either date is missing, then Time to cessation of symptoms is missing.

 $\it Time\ to\ cess at ion\ of\ symptoms = (Date\ and\ time\ of\ cess at ion\ of\ symptoms - Date\ and\ time\ of\ first$

treatment administered)

Time to recurrence of HL lesions: It is the time (in days) from resolution of the cold sore treated in the Treatment phase until appearance of a cold sore during the follow-up period. The time to first recurrence is determined by assessment from the investigator and documented using NRS symptom scores and face images using the Science 37 Platform. For subjects who do not recur during the follow-up period, the data will be censored at the time of last follow-up.

Time to recurrence of HL lesions (Days) = (Date of first recurrence of HL lesions – Date of healing of primary lesions) + 1

CONFIDENTIAL Page 18 of 31

Private and Confidential Study No 21755 Date: DEC 18, 2023

Treatment Emergent Adverse Event: A TEAE is defined as any new AE that commences on or after the start of the first study drug administration or any pre-existed AE/ condition that worsened in severity following administration of study drug.

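### The SAP healing rule for non-vesicular lesions does not require the normal-lip score to follow a visible sign, so the primary endpoint can be dated before the lesion has cleared

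*SAP*

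**What the plan says.** The primary endpoint is duration of episode (DOE). SAP 5.1 and 7.7.1 refer to SAP Section 4 for its definition, and that section treats the endpoint at two levels.

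- **Concept.** For vesicular lesions DOE ends at "healing of primary lesions (loss of crust) for subjects who experience a vesicular lesion". For the others, "DOE is the time from study intervention initiation to the return to normal skin as determined by the independent blinded reader", or at cessation of symptoms if that is later.
- **Scoring rule.** A vesicular lesion has healed when its image score "drops to either 0 or 1 after progressing to 3 and beyond". For a lesion that never reaches 3, the rule reads: "defined as a face image interpretation Likert score of 0 or cessation of symptoms i.e., all NRS symptom scores as 0, whichever comes last".

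The image scale (Protocol 8.2.4, SAP 9.4) runs from 0 for a normal lip, through 1 for erythema and 2 for a papule, to 3 and above for vesicle, ulcer and crust. SAP 2.2 asks participants to "self-initiate treatment (study intervention) preferably within one hour and before the visible appearance of any signs of HL lesions". Protocol 8.1.4 adds: "Participants must always record pre-dose NRS and a face image irrespective of the start time of prodromal symptoms". After dosing, readings come three times a day: "Face images taken at 09:00, 14:00 and 19:00 each day" (Protocol 1.3), with NRS scores at the same times. SAP 3.3 covers healed participants whose "healing ending date and time are missing", but neither document says how that date is chosen from repeated readings.

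**The concern.** The vesicular rule contains an order: the score must first rise to 3 or more and then fall. The non-vesicular rule contains none. The design asks for dosing before visible signs, so a score of 0 at and shortly after dosing is expected, and that 0 already meets the image half. The other half is met when all NRS items reach 0. A program that takes the first qualifying time for each half, and then the later of the two, can therefore end the episode while a score of 1 or 2 is still being recorded. That is not a return to normal skin.

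A second, weaker gap applies to both lesion types. With three readings a day, the rule should say whether one qualifying reading is enough or whether it must be confirmed. It says neither.

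What is at stake is the event time of the primary endpoint: the same images and scores can yield different DOE values. The healing date also starts the clock for time to recurrence, but there a shift of 24 to 72 h is only 1 to 3 days against 12 months.

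**Working it through.** The plan gives no figure to reproduce here, and the sample-size text is redacted. The check applies the rule to constructed reading sequences. The sequences are assumptions; the reading times and score meanings come from the documents.

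**Clock.** Dosing is set at 08:00 on Day 1, with readings at 09:00, 14:00 and 19:00 on Days 1 to 14 (3 × 14 = 42). Hours since dosing = (day − 1) × 24 + clock hour − 8. At 09:00 this gives Day 3 = 49, Day 4 = 73, Day 5 = 97, Day 6 = 121 and Day 7 = 145.

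**Two derivations.**
- *First-qualifying*: the later of (first image 0) and (first all-zero NRS), each dated separately.
- *Return after sign*: the first reading after the last score of 1 or 2 at which the image is 0 and all NRS items are 0.

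**Non-vesicular episode.** Image 0 on Days 1–2, papule on Days 3–5, image 0 from 09:00 on Day 6.

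| NRS all zero from 09:00 on | First-qualifying (h) | Return after sign (h) | Early by (h) |
|---|---|---|---|
| Day 3 | 49 | 121 | 72 |
| Day 4 | 73 | 121 | 48 |
| Day 5 | 97 | 121 | 24 |
| Day 6 | 121 | 121 | 0 |
| Day 7 | 145 | 145 | 0 |

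Two variants show no error, both with symptoms at zero from Day 4. If the papule is already present at dosing and lasts through Day 5, both derivations give 121 h. If no sign is ever visible, cessation of symptoms sets the time and both give 73 h.

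The error therefore needs all three of: an image 0 before the first sign, a later sign that never reaches 3, and symptoms at zero before that sign clears.

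**Why both halves must hold at the same reading.** Take the same images, with NRS all zero on Day 2 only, symptoms back on Days 3–7, and zero again from 09:00 on Day 8.
- First-qualifying: Day 2 09:00 = 24 + 1 = 25 h.
- Order required, but halves dated separately: the later of 121 and 25 = 121 h, with symptoms still present.
- Both halves at one reading, but no order required: 25 h again.
- Order required and both halves at one reading: Day 8 09:00 = 7 × 24 + 1 = 169 h.

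Neither condition is enough alone.

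**Single versus confirmed reading, vesicular lesion.** Crust on Days 4–8, clear from 09:00 on Day 9 = 8 × 24 + 1 = 193 h. A single stray score of 1 at 09:00 on Day 5 gives 97 h (193 − 97 = 96 h early). At 14:00 on Day 6 it gives 5 × 24 + 6 = 126 h (193 − 126 = 67 h early). With no stray score both conventions give 193 h. The documents give no rate for such readings.

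**The case against.** **The adjoining definition supplies the order.** One cannot return to a state that was never left, and loss of crust is hard to claim if crust is scored again at the next reading. This stands as evidence of intent. It does not remove the gap, because the scoring rule is what will be programmed, and it states an order for one lesion type and omits it for the other.

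**A benign reading exists.** If the phrase about whichever comes last means that both conditions hold at one reading, the Day 3 to Day 5 rows above all become 121 h. That is a fair reading. The text does not state it, and it still fails when symptoms pause before the sign appears (25 h in the example).

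**Healing may be a recorded date.** The SAP treats the healing date as something that can be missing, and it is to be read with an eCRF that is not available here. A first-qualifying algorithm might then never be run. Section 4 also assigns the determination of normal skin to the independent blinded reader. Both points stand, but neither says which of several qualifying readings sets the date.

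**Stronger readings a reader might infer.**
- *An early normal image ends the episode by itself.* It does not, because all NRS items must also be 0.
- *The treatment comparison is biased.* Each such error shortens an individual DOE, but nothing in the documents shows how often it occurs or in which arm.
- *Shifts of 24 to 72 h swamp the 0.57-day reduction reported for the earlier trial (Protocol 2.2).* That compares a single participant's error with a group difference on another endpoint.
- *Vesicular healing is wrongly defined.* That rule has its order; the example depends on a stray score of unknown frequency.

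**Conclusion.** The point holds for non-vesicular lesions. The rule as written allows a primary-endpoint time that conflicts with the definition it serves. In the constructed episodes the error is 24, 48 or 72 h for a participant who meets all three conditions, and zero otherwise. These sizes rest on an assumed dosing time, assumed lesion courses and a first-qualifying derivation. The effect on the log-rank test or the hazard ratio cannot be derived from the documents. The single-versus-confirmed question is a convention still to be stated, not an error in the rule. Weight: minor to should-fix. It is worth settling because it concerns the primary endpoint and the correction is nearly free.

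**What to change.** Amend SAP Section 4 before unblinding.

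1. For non-vesicular lesions, date healing at the first reading at which the image score is 0, following the last pre-dose or post-dose score of 1 or 2, and all five NRS items listed in Section 4 are 0 at that same reading.
2. If no image ever scores above 0, set DOE to the time to cessation of symptoms.
3. For both lesion types, state whether a single or a confirmed qualifying reading counts, and report the other as a sensitivity analysis. The choice of confirmation convention is the sponsor's.
4. If healing is captured as a recorded date, state that it follows the same rule.
5. Say what happens when an image or an NRS set is missing at a reading.

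The cost is wording and slightly more derivation code. No new data are needed, because the pre-dose image is already mandatory. One downside: anchoring on the last score of 1 or 2 means that an isolated late score of 1 postpones healing, or leaves the participant censored at 14 × 24 = 336 h.

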End of Treatment Phase: The end of the Treatment Phase for a subject is defined as the date (time) of the last visit in the Treatment Phase.

End of Study: The end of the study is defined as the date of the last follow-up visit (either by documented HL outbreak or at 12 months) of the subject in the study. A subject is considered to have completed the study if he/she has completed all phases of the study up to Follow up Phase.

Aborted Lesion: It is defined as a treated HL lesions that do not progress to the vesicular or crust stage. A lesion that returns to normal skin without forming a vesicle or crust will be counted as an aborted lesion i.e., for this lesion the face image interpretation Likert score will be less than or equal 2 and will never reach a score of 3 or above before healing.

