7.7.2 Analysis of Secondary Efficacy Endpoints

- ➤ Incidence of aborted lesions, defined as treated HL lesions that do not progress to the vesicular or crust stage. A lesion that returns to normal skin without forming a vesicle or crust will be counted as an aborted lesion. Observation period to determine healing will last up to 14 days. The incidence(events) of aborted lesions will be reported by treatment groups and proportions of subjects with at least one Incidence of Aborted Lesions will be compared between the two treatment groups using the Chi square or Fisher's Exact test for categorical data for both ITT and PP populations. Individual subject data for aborted lesions will be presented in Listing.
- ➤ Incidence of recurrence of HL lesions during the 12-month follow-up period will be reported by treatment groups for FU population. Recurrence is determined by assessment from the investigator and documented using NRS symptom scores and face images using the Science 37 Platform.

The percentage of subjects with at least one recurrence of HL lesions during the 12-month follow-up period will be compared between the two treatment groups using the Chi square or Fisher's Exact test for homogeneity of proportions for categorical data using FU population.

CONFIDENTIAL Page 23 of 31

Private and Confidential Study No 21755 Date: DEC 18, 2023

Individual subject data for recurrence of HL lesions will be presented in Listing.

> Time to recurrence of HL lesions, measured in days from resolution of the cold sore treated in the Treatment phase until appearance of a cold sore during the follow-up period. For subjects who do not recur during the follow-up period, the data will be censored at the time of last follow-up. Time to recurrence of HL lesions will be analyzed similarly to the analysis of primary endpoint using KM method for FU population. Individual subject data Listing for time to recurrence of HL lesions will be presented.

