9.4 Face Image Interpretation

Subjects face images pre- and post-study intervention will be evaluated by an independent reader blinded to the study intervention administered. Lesion interpretation will be done using a 6-point Likert scale.

- 0 = Normal lip
- 1 = Erythema
- 2 = Papule
- 3 = Vesicle
- 4 = Ulcer
- 5 = Crust

CONFIDENTIAL Page 31 of 31

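### The aborted-lesion comparison makes no use of the blinded pre-dose image, so anyone already at score 3 or above before dosing can only count as not aborted; a stratified or at-risk analysis is a cheap improvement

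*SAP*

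**What the plan says.** **Definition.** SAP section 4 says of an aborted lesion: "It is defined as a treated HL lesions that do not progress to the vesicular or crust stage". In terms of the image score, it requires that "the face image interpretation Likert score will be less than or equal 2 and will never reach a score of 3 or above before healing". The same section defines the complement: "A lesion will be categorised as vesicular if a subject has face image interpretation Likert scale score of 3 or above". Neither rule refers to the score before dosing.

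**Pre-dose image.** Protocol 8.1.4 makes it compulsory: "Participants must always record pre-dose NRS and a face image irrespective of the start time of prodromal symptoms in the Science 37 Platform". SAP 9.4 has it scored on the same 0 to 5 scale: "Subjects face images pre- and post-study intervention will be evaluated by an independent reader blinded to the study intervention administered".

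**Timing of dosing.** SAP 2.2 has participants treat themselves "preferably within one hour and before the visible appearance of any signs of HL lesions according to the product instructions". This is a preference. No exclusion criterion in Protocol 5.2 concerns a visible lesion at the time of dosing.

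**Analysis.** SAP 7.7.2 compares the proportions with aborted lesions by chi-square or Fisher's exact test, "for categorical data for both ITT and PP populations". Under SAP 6.1, ITT requires one post-dose image score. PP further requires 14 days of evaluations and no major violation, and major is not defined by lesion stage. SAP 7.11 plans no subgroup analyses.

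**The concern.** The endpoint asks whether a treated lesion goes on to the vesicular or crust stage. A lesion already at that stage when the tablet is applied cannot answer the question, yet it stays in the denominator as a failure in whichever arm it falls. The secondary objective concerns abortion after prodromal symptoms, so these participants carry no information about the effect it describes.

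At stake are a smaller difference in proportions, some loss of power on one secondary endpoint, and added noise if the share of such participants differs between arms by chance. The information needed to deal with this is already collected before treatment and read blinded. The primary endpoint is not part of this point.

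**Working it through.** The published sample-size text is redacted and no abortion rate is given, so there is no planned figure to reproduce. The inputs below are assumptions unless a source is named.

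**Inputs**
- Two-sided 5% test, no multiplicity adjustment (SAP 3.1); 1:1 allocation (SAP 2.4).
- f: share with a pre-dose score of 3 or above, taken as equal in both arms. Not in the documents; shown from 2% to 20%.
- Abortion rates among those still at risk: 25% placebo, 35% active (assumed).
- 250 participants per arm (assumed).

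**Step 1, effect size.** Each arm's observed rate is (1−f)·p.
- Difference = (1−f)(p_active − p_placebo). At f = 10%: 0.315 − 0.225 = 0.090, against 0.100 among those at risk.
- Ratio = (1−f)·p_active / [(1−f)·p_placebo] = 0.35/0.25 = 1.40 for every f.

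**Step 2, power.** Power = Φ[(d − 1.96·SE0)/SE1], where d is the difference in rates, SE0 uses the pooled rate and SE1 the two separate rates. Keeping everyone uses n = 250 and the diluted rates. Setting the not-at-risk aside uses n = 250(1−f) and the undiluted rates.

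At f = 20%:
- Kept: 20% vs 28%, n = 250; (0.08 − 1.96 × 0.03820)/0.03803 = 0.135, power 55.4%.
- At-risk only: 25% vs 35%, n = 200; (0.10 − 1.96 × 0.04583)/0.04555 = 0.224, power 58.8%.

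| f | Difference, all kept (points) | Power, all kept | Power, at-risk only | Gain (points, before rounding) |
|---|---|---|---|---|
| 0% | 10.0 | 68.5% | 68.5% | 0 |
| 2% | 9.8 | 67.3% | 67.7% | 0.4 |
| 5% | 9.5 | 65.4% | 66.3% | 0.9 |
| 10% | 9.0 | 62.1% | 63.9% | 1.8 |
| 20% | 8.0 | 55.4% | 58.8% | 3.5 |

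Most of the lost power cannot be recovered, because the at-risk sample is itself smaller. At f = 20% the loss from f = 0 is about 13 points, of which 3.5 come back.

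**Step 3, chance imbalance.** Suppose f is 8% on placebo and 12% on active. The difference is 0.35 × 0.88 − 0.25 × 0.92 = 7.8 points. Reversed, it is 0.35 × 0.92 − 0.25 × 0.88 = 10.2. The balanced value at 10% is 9.0. With 250 per arm the standard error of the imbalance is √(2 × 0.10 × 0.90/250) = 2.7 points, so a 4-point gap would not be unusual.

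**Step 4, stratified test.** In a CMH test split at pre-dose score 2 or less versus 3 or above, the upper stratum has no events. It adds nothing to the numerator or the variance, so the test is essentially the at-risk comparison while every participant stays in the analysis set.

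**The case against.** **Frequency.** A reader might infer that the plan expects many participants to have vesicles at dosing, because SAP 7.7.3 analyses those dosing more than 1 hour after prodrome onset as a group. The documents do not support that. Late dosing is not the same as a visible vesicle, and nothing links the two. Protocol 6.1 and 8.1.2 tell participants to treat at the first prodromal symptoms, which makes a small f plausible. This objection stands.

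**Scale.** A reader might also infer that the treatment effect is diluted however it is measured. With equal f the risk ratio is unchanged, and SAP 7.7.2 names no effect measure for this endpoint, only a comparison of proportions. The shrinkage applies to the difference, and the power effect to the test. This also stands.

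**PP.** It is tempting to say that PP certainly keeps these participants. Late dosing is recorded as a deviation (Protocol 6.1 and 6.5), eligibility is reviewed again at Visit 2, and major violations are settled before lock. The documents neither class these cases as major nor rule it out. Retention is certain only for ITT.

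**Choice of target.** The trial studies self-initiated treatment, and the effect in everyone who treated a lesion is a legitimate quantity. Protocol 9.3 assigns PP and ITT to the secondary efficacy endpoints, so replacing them outright would depart from the protocol. That argues for adding an analysis beside them. It does not remove the case for one.

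**Missing images.** A restriction with no missing-data rule could go wrong. SAP section 4 takes baseline as the last non-missing pre-dose assessment. If the Day 1 image were missing, the symptom-free screening image could stand in and a late-stage lesion would pass as at risk. This stands, and the fix must cover it.

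**Conclusion.** The structural point holds. Under the natural reading of the definition, an ITT participant already at score 3 or above before dosing is a fixed non-event, and nothing planned separates such participants out. The same applies to PP unless they are classed as major violators.

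The size is unknown and probably modest: a factor of (1−f) on the difference, none on the risk ratio, and roughly 0.4 to 3.5 points of recoverable power for f from 2% to 20%. The power figures rest on the assumed 250 per arm and rates of 25% and 35%, and on equal f in both arms. The documents do not support calling the planned ITT and PP comparison invalid or seriously biased, nor replacing it.

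One ambiguity remains at any f. The SAP does not say whether the pre-dose image itself counts towards reaching a score of 3. If only post-dose images counted, a lesion already at that stage could be scored as aborted when later images are missing or clear quickly. The rule should be stated. Overall this is a low-cost improvement to consider, not a defect that threatens the trial.

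**What to change.** Keep the ITT and PP comparisons and, before unblinding:

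- Either stratify the aborted-lesion test by Day 1 pre-dose score (2 or less versus 3 or above, CMH), or add a pre-specified analysis restricted to a Day 1 pre-dose score of 2 or less. The score precedes treatment and is read blinded, so either option preserves the randomized comparison.
- Report the share at 3 or above before dosing, by arm.
- State in SAP section 4 that the Day 1 pre-dose image, not the screening image, decides at-risk status. State also whether it counts in the aborted-lesion definition.
- State how missing or unreadable Day 1 pre-dose images are classified.
- List the change in SAP 7.13, since Protocol 9.4.3 specifies a chi-square test and Protocol 9.3 the populations.

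Cost: a few sentences in the SAP, one extra table and a slightly smaller denominator for the at-risk analysis. No new data are needed.
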